- ^g The platelet measurement for eligibility must be taken within 96 hours of start of infusion. Platelet sample may be combined with safety labs if sample is taken at the same time. All scheduled platelet measurements must be sent to the central and local lab. If there is insufficient time to review the central lab results an additional local lab sample may be obtained in order to assess eligibility for infusion.
- ^h Women of childbearing potential, only. Urine test on Day -1 for Day 1 prior to infusion; serum test during Screening and on Day 29. Central lab should assess serum sample collected at screening and on Day 29, but the local lab can assess the urine test on Day -1/Day 1 prior to the infusion.
- ¹ Duplicate samples for IgG should not be drawn if sample was already taken with safety labs collection.
- ^j Duration of infusion is based on dosing instructions (details provided in the pharmacy manual). Patients will be required to drink 2 glasses of liquid in the morning before the start of infusion. Just before infusion, patients will be provided the opportunity to urinate. Patients receiving M254 or IVIg can be discharged 4 hours post-infusion.
- k If infusion duration is <20 minutes, end of infusion activities may be scheduled as logistically feasible with the PK sample drawn from 1 minute before the end of infusion to 2 minutes after the end of infusion. For infusion durations ≥20 minutes, activities should occur in the order of the table (top to bottom) unless a footnote indicates otherwise.
- All systemic infusion reactions and associated AEs will be graded using Common Terminology Criteria for Adverse Events (CTCAE).
- ^m Patients with ITP may admit to the unit the morning of Day 1so any procedure specified on Day -1 can occur on Day 1, but all results must be back before infusion begins. Likewise, any pre-infusion assessment specified on Day 1 can occur on Day -1 and does not need to be duplicated.
- ⁿ Study staff should follow-up with the patient approximately 12 hours post-discharge for safety via phone call.
- ^o Discharge from study after final study period unless further follow-up of open AEs is deemed necessary by the Investigator.
- P M254 or IVIg infusion will occur on this day if patient's platelet count meets criteria, and then the Schedule of Activities should be followed starting at Day 1. For Period 2, Day 1, any assessments completed on the same date for Period 1 follow-up do not need to be duplicated.
- ^q Blood sample for PK is required during the M254 treatment period only. It is NOT needed for the IVIg treatment period.

Statistical Analysis Plan MMT102EC-170091 Protocol: MOM-M254-001 Version 2 Date: 14-Jul-2021

- ¹ ITP-BAT to be completed separately at Day 1 and 29 of each period (M254- and IVIg-treatment). Only 1 ITP-BAT assessment is needed if Day 29 of the first period is the same as Day 1 of the second period.
- ⁵ ECG and vital signs assessments required at the end of the infusion may be initiated 15 minutes prior to the end of infusion
- t These should be conducted as abbreviated physical exams
- ^u PK sample is required prior to the start of infusion (on the day of the infusion).
- ^v Biomarker samples are collected at pre-infusion, Day 2, and Day 8; ADA samples are collected at pre-infusion and Day 29 follow-up. Please refer to the lab manual for specific instructions.

Statistical Analysis Plan MMT102EC-170091 Protocol: MOM-M254-001 Version 2 Date: 14-Jul-2021

Day (M254 Naïve)	-28 to -2	-1 °	1-54	57 ±3	71 ±3
Day (Part B/C Patients)	-28 to -2	-1 ^{a, o}	1-40	43 ±3	57 ±3
	Screening ^b	Pre- infusion		Post- infusion	Follow-up
Procedure ^c Hour		0		0	0
Informed Consent	x	12 X			
Demographics	X	20		9 9	
Prior/Concomitant Medications ^g	х	X		x	X
AE Assessment ^g	X	X	1	x	X
ITP-BAT ^s		x			
Medical History	x				
Inclusion/Exclusion Criteria	х	x			
Physical Examination	Х	Xu	e D2	s	Xu
Drug Screening	х		Table		
Body Weight ^e	Х	x	See		X
Height and Body Mass Index	X		22240-442		
Vital signs ^{f, t}	X	x		x	X
12-lead ECG ⁺	X	x			Х
Safety Labs ^h	X	X		х	Х
Serology: HBsAg, anti-HCV, anti-HIV 1 and 2	Х			8	
Platelet Count ⁱ	X	x		x	X
Bloodtype, if unknown	x				

Table 1-4. Part D Schedule of Activities (USA sites included)

Statistical Analysis Plan MMT102EC-170091 Protocol: MOM-M254-001 Version 2 Date: 14-Jul-2021

Day (I	M254 Naïve)	-28 to -2	-1 °	1-54	57 ±3	71 ±3
Day (Part E	B/C Patients)	-28 to -2	-1 ^{a, o}	1-40	43 ±3	57 ±3
		Screening ^b	Pre- infusion		Post- infusion	Follow-up
Procedure ^c	Hour		0		0	0
Platelet Autoantibodies, if unknow	vn	Х				
Total IgG ^k		х	X		X	x
Blood Samples for PK ¹					X	X
Blood Samples for ADA ^x		,	X	10		Х
Urinalysis		Х	X		X	Х
Pregnancy Test ^j		Х	X			Х
Infusion Reaction ⁿ			x			Х
Discharge from Study						Xq

Table 1-4. Part D Schedule of Activities (USA sites included)

Footnotes are described on the last page of Table D2.

Statistical Analysis Plan MMT102EC-170091 Protocol: MOM-M254-001 Version 2 Date: 14-Jul-2021

TADIC D2 (USA SILES III	ciudeu)		2	25	-2	16	25	12	32	\$S	¥2	12	85 C
	1°	1	1	1	1	1	2	3 ^d	4 ^d	5 d	8±1 ^d	10±3 ^d	12±3 d
Day (M254 Naïve)	15±1°	15	15	15	15	15	~	SI	cip ^w	£.	22±1 d	Sk	dp ^w
All visit windows are relative	29±1°	29	29	29	29	29		SI	cip ^w		36±1 ^d	Sk	сір ^w
	43±1°	43	43	43	43	43	44	45 ^d	46 ^d	47 ^d	50±1 ^d	52±3 ^d	54±3 ^d
Day (Part B/C Patients)	1 ^{a, o}	1	1	1	1	1	2	3 d	4 ^d	5 ^d	8±1 d	10±3 ^d	12±3 ^d
All visit windows are relative	15±1°	15	15	15	15	15	10	SI	cip ^w		22±1 d	Sk	^{tip^w}
to the most recent dose	29±1°	29	29	29	29	29	30	31 ^d	32 ^d	33 d	36±1 ^d	38±3 ^d	40±3 ^d
	Infusion	2000 - 100 		112	2		Post-	infusion	(20) (20)	25	11-	ii.	10
Procedure ^c Hour	0	0 (end of infusion)	0.25	0.5	2	4	0	0	0	0	0	0	0
Unit Admit	x												
Prior/Concomitant Medications	x	x	x	x	x	x	x	x	x	x	x	x	x
AE Assessment ^g	x	x	x	x	X	x	X	x	x	x	X	x	x
Vital signs ^{f, t}	X	X	х	x	x	x	x	X	x	x	X	X	x
12-lead ECG ^t		X	х	x	x	X	2	20	2				20
Safety Labs ^h	X			2	3	X	X	28	9		X	×.	C.
Platelet Count ⁱ	X					X	X	X	x	X	X	X	x
Total IgG ^k	X		Х			X	x			x	X		
Blood Samples for PK ¹	Xv	X	X			X	x			x	X		
Urinalysis	X					X	x				Х		
M254 IV Infusion ¹	X ^r (start)	X ^m (end)											
Infusion Reaction ⁿ	X	X	X	x	X	X	x		2				
Unit Discharge						Xp							
					and a second								

Table D2 (USA sites included)

ADA = anti-drug antibody; AE = adverse event; ECG = electrocardiogram; HBsAg = hepatitis B surface antigen; HCV = hepatitis C virus; HIV = human immunodeficiency virus; IgG = immunoglobulin G; ITP-BAT = immune thrombocytopenic purpura bleeding assessment tool; IV = intravenous; PK = pharmacokinetics.

Statistical Analysis Plan MMT102EC-170091 Protocol: MOM-M254-001 Version 2 Date: 14-Jul-2021

- ^a Patients continuing from Part C may have the procedures from Part C, Period 2, Day 29 (or the last day of Part C, Period 2 if follow-up is extended for any reason); Part D, Day -1, and Part D, Day 1 combined into a single visit, if preferred and if logistics for assessment allow.
- ^b See Section 5 for the screening requirements for patients transitioning from Part B or C to Part D.
- ^c Procedures should occur in the order presented above from top to bottom if more than 1 procedure occurs at the same nominal time. Urine sampling or anything with a specific footnote may be done out of order.
- ^d Only visits required to be at the study site are screening, infusions, the day after an infusion, and the last follow-up, all others can be done by visiting nurse if patient prefers this option. Visit windows of ±1 day should be used whenever possible; ±3 day windows should only be used when required due to clinical site closures (eg, for holidays or COVID-19-related limited schedules). When visit windows overlap, they must not be combined into a single actual day.
- e Screening weight will be used to determine eligibility and dosing, and will allow up to 1 month for weight variability.
- f Vital signs includes body temperature, supine (after 5 minutes) blood pressure, pulse rate, and respiratory rate. Vital signs will be assessed every 30 minutes during an infusion. For infusions <35 minutes, vital signs assessments may occur just after starting the infusion and just prior to the end of the infusion. Refer to Footnote t for exception.

- ^g Concomitant Medications and AEs will be assessed throughout the infusion and the study. Subjects will be queried and observed for AEs daily during the confinement period, then at each subsequent clinic visit. Should there be a bleeding event reported by the patient or observed by the physician during examination, the ITP-BAT must be completed, see ITP-BAT in Appendix 6, as well as an AE form.
- ^h Safety labs will include complete blood count (CBC), serum chemistry, coagulation, and coagulation screening lab (at screening only) (see Table 10-1). All safety labs will assessed by the Central lab, except for platelet counts, which should be done locally at all the visits where they are scheduled. In case of an AE that requires additional sampling and the Investigator needs to review the results to determine patient care, additional safety labs can be assessed by the local lab.
- ⁱ The platelet measurement for eligibility must be taken within 96 hours of start of infusion. Platelet sample may be combined with safety labs if sample is taken at the same time. All scheduled platelet measurements must be sent to the local and central lab. If there is insufficient time to review the central lab results an additional local lab sample may be obtained in order to assess eligibility for infusion.
- ^j Women of childbearing potential, only. Urine test on Day -1; serum test during Screening and on Day 29. Central lab should assess serum sample collected at screening and on final follow-up, but the local lab can assess the urine test on Day 1/Day 1 prior to the infusion.
- ^k Duplicate samples for IgG should not be drawn if sample was already taken with safety labs collection.
- ¹ Duration of infusion is based on dosing instructions (details provided in the pharmacy manual). Patients will be required to drink 2 glasses of liquid in the morning before the start of infusion. Just before infusion, patients will be provided the opportunity to urinate. Patients receiving M254 can be discharged 4 hours post-infusion.
- ^m If infusion duration is <20 minutes, end of infusion activities may be scheduled as logistically feasible with the PK sample drawn from 1 minute before the end of infusion to 2 minutes after the end of infusion. For infusion durations ≥20 minutes, activities should occur in the order of the table (top to bottom).

- n All systemic infusion reactions and associated AEs will be graded using Common Terminology Criteria for Adverse Events (CTCAE).
- Patients with ITP may be admitted to the unit the morning of Day 1 instead of Day -1. Any procedure specified on Day -1 can occur on Day 1, but all results must be back before infusion begins. Likewise, any pre-infusion assessment specified on Day 1 can occur on Day -1 and does not need to be duplicated.
- P Study staff should follow-up with the patient approximately 12 hours post-discharge for safety via phone call.
- ^q Discharge from study after final study period unless further follow-up of open AEs is deemed necessary by the Investigator.
- I M254 infusion will occur on this day if patient's platelet count meets criteria, and then the Schedule of Activities should be followed starting from whichever infusion the patient is scheduled for in Part D, ie, 2nd, 3rd, or 4th. Any assessments completed on the same date from the prior infusion period follow-up do not need to be duplicated.

Statistical Analysis Plan MMT102EC-170091 Protocol: MOM-M254-001 Version 2 Date: 14-Jul-2021

- ^s ITP-BAT to be completed at Day 1 prior to infusion.
- t ECG and vital sign assessments required at the end of the infusion may be initiated 15 minutes prior to the end of infusion
- ^u These should be conducted as abbreviated physical exams
- ^v PK sample is required prior to the start of infusion (on the day of the infusion).
- ^w Skip indicates that no assessments occur on these days.
- x ADA samples are collected at each pre-infusion and the final follow-up visit. Please refer to the lab manual for specific instructions.

Appendix 3: List of In-Text Outputs

The planned tables, figures and subject data listings for the CSR are listed below. The placement and numbering presented is for tracking / development purpose and may deviate from the placement order and numbering listed in the CSR. This list defines the tables to be produced by programming. The Medical Writer can decide to insert any of the figures or create more tables for the CSR text independently of this plan.

List of CSR In-Text Tables and Figures:					
TFL Section	Output Type	Title	Population Set		
14.1	Table	Subject Demographics and Characteristics	Randomized		
	Table	Extent of Exposure	Safety		
14.2	Figure	Arithmetic Mean PK Serum Concentrations	РК		
	Table	Summary of PK Parameters	РК		
	Figure	Dose normalized PK Parameters versus Dose	РК		
	Table	Summary of Platelet Counts (Absolute Values and Changes from Baseline)	FAS/PP		
	Figure	Arithmetic Platelet Counts (Absolute Values and Changes from Baseline)	FAS/PP		
14.3	Table	Summary of all TEAEs by System Organ Class and Preferred Term	Safety/PP		
	Table	Related TEAEs by System Organ Class and Preferred Term per Study Part and Treatment	Safety/PP		
	Table	SAE by SOC, PT per Study Part and Treatment	Safety/PP		
	Table	TEAEs of Special Interest by System Organ Class and Preferred Term per Study Part and Treatment	Safety/PP		
	Table	Summary of TEAEs by Relationship, per Study Part and Treatment	Safety/PP		
	Table	Summary of TEAEs by Severity, per Study Part and Treatment	Safety/PP		

Appendix 4: List of End of Text Outputs

List of End of Text Tables and Figures:				
Output	Title	Population Set	Interim (Y/N)	
Section 14.1 – Dis	position and Demographic Data			
Table 14.1.1	Summary of Subject Disposition – Part A, B, C, D	Safety		
Table 14.1.2.1	Summary of Demographics – Part A, B, C, D	Safety/PP		
Section 14.2 – Pha	armacokinetic Data and Pharmacodynamic Data			
14.2.1 Pharmacok	inetic Data			
Table 14.2.1.1	Individual Values and Descriptive Statistics of M254 Serum Concentrations - Part A, B, C, D	РК		
Table 14.2.1.2	Individual Values and Descriptive Statistics of Total IgG Serum Levels Absolute Values - Part A, B, C, D	PK		
Table 14.2.1.3	Individual Values and Descriptive Statistics of Total IgG Serum Levels Changes from Baseline - Part A, B, C, D	РК		
Table 14.2.1.4	Individual Values and Descriptive Statistics of M254 Serum PK Parameters - Part A, B, C, D	РК		
Table 14.2.1.5	Individual Values and Descriptive Statistics of Total IgG Serum PK Parameters - Part A, B, C, D	РК		
Figure 14.2.1.6	Median M254 Serum Concentrations versus Time Profile (Linear and Semi-logarithmic) - Part A, B, C, D	РК		
Figure 14.2.1.7	Median Total IgG Serum Levels Absolute Values versus Time Profile (Linear and Semi-logarithmic) - Part A, B, C, D	РК		
Figure 14.2.1.8	Median Total IgG Serum Levels Changes from Baseline versus Time Profile (Linear and Semi- logarithmic) - Part A, B, C, D	РК		
Figure 14.2.1.9	Combined Individual M254 Serum Concentrations versus Time Profile (Linear and Semi-logarithmic) – Part A, B, C, D	РК		
Figure 14.2.1.10	Combined Individual Total IgG Serum Levels Absolute Values versus Time Profile (Linear and Semi-logarithmic) – Part A, B, C, D	РК		
Figure 14.2.1.11	Combined Individual Total IgG Serum Levels Changes from Baseline versus Time Profile (Linear and Semi-logarithmic) – Part A, B, C, D	РК		
Figure 14.2.1.12	Individual M254 Serum Concentrations versus Time Profile (Linear and Semi-logarithmic) - Part A, B, C, D	Safety		

Figure 14.2.1.13	Individual Total IgG Serum Levels Absolute Values versus Time Profile (Linear and Semi-logarithmic) - Part A, B, C, D	Safety
Figure 14.2.1.14	Individual Total IgG Serum Levels Changes from Baseline versus Time Profile (Linear and Semi- logarithmic) - Part A, B, C, D	Safety
Figure 14.2.1.15	Dose Normalized (mg/kg) PK Serum Parameters vs Dose - Part A, B	РК
Section 14.2.2 – P	harmacodynamic Data	
14.2.2.1 Platelet C	ounts	
Table 14. 2 .2.1 .1	Individual Values and Descriptive Statistics of Platelet Counts – Part B, C, D	FAS/PP
Table 14. 2.2.1.2	Individual Values and Descriptive Statistics of Platelet PD Parameters – Part B, C, D	FAS/PP
Table 14. 2.2.1 .3	Primary Statistical Platelet PD Parameters Analysis: Efficacy Analysis of M254 vs IVIg PD Parameters Ratios – Part C	FAS
Table 14. 2 .2.1 .4	Frequency counts of the responders and non responders	FAS/PP
Table 14. 2.2.1 .5	Secondary Statistical Platelet PD Parameters Analysis: Overall Platelet Response Rate – Part B, C, D	FAS/PP
Figure 14. 2.2.1 .6	Arithmetic Mean Platelet Counts Absolute Values versus Time Profile (Linear and Semi-logarithmic) - Part B, C, D	FAS/PP
Figure 14. 2.2.1 .7	Arithmetic Mean Platelet Counts Changes from Baseline versus Time Profile (Linear and Semi- logarithmic) - Part B, C, D	FAS/PP
Figure 14. 2.2.1 .8	Arithmetic Mean Platelet Counts % Changes from Baseline versus Time Profile (Linear and Semi- logarithmic) - Part B, C, D	FAS/PP
Figure 14. 2.2.1 .9	Combined Individual Platelet Counts Absolute Values versus Time Profile (Linear and Semi-logarithmic) – Part B, C, D	FAS
Figure 14. 2.2.1.10	Combined Individual Platelet Counts Changes from Baseline versus Time Profile (Linear and Semi- logarithmic) – Part B, C, D	FAS
Figure 14. 2.2.1 .11	Combined Individual Platelet Counts % Changes from Baseline versus Time Profile (Linear and Semi- logarithmic) – Part B, C, D	FAS
Figure 14. 2.2.1 .12	Individual Platelet Counts Absolute Values versus Time Profile (Linear and Semi-logarithmic) - Part B, C, D	FAS

Figure 14. 2.2.1 .13	Individual Platelet Counts Changes from Baseline versus Time Profile (Linear and Semi-logarithmic) - Part B, C, D	FAS	
Figure 14. 2.2.1 .14	Individual Platelet Counts % Changes from Baseline versus Time Profile (Linear and Semi-logarithmic) - Part B, C, D	FAS	
Section 14.3 – Saf	ety Data		
14.3.1 Adverse Ev	rents		
Table 14.3.1.1	Overview TEAE	Safety	Y ¹
Table 14.3.1.2	Summary of Treatment-Emergent Adverse Events by System Organ Class and Preferred Term – Part A, B, C, D	Safety	Y ¹
Table 14.3.1.3	Summary of Related Treatment-Emergent Adverse Events by System Organ Class and Preferred Term – Part A, B, C, D	Safety	Y ¹
Table 14.3.1.4	Summary of Serious Adverse Events by System Organ Class and Preferred Term – Part A, B, C, D	Safety	Y ¹
Table 14.3.1.5	Summary of Adverse Events of Special Interest by System Organ Class and Preferred Term – Part A, B, C, D	Safety	Y ¹
Table 14.3.1.6	Summary of Treatment-Emergent Adverse Events by Relationship to Study Drug – Part A, B, C, D	Safety	Y ¹
Table 14.3.1.7	Summary of Treatment-Emergent Adverse Events by Severity – Part A, B, C, D	Safety	Y ¹
14.3.2 Deaths, Oth	ner Serious And Significant Adverse Events		
Table 14.3.2	Listing of Deaths and Other Serious Adverse Events		Y ¹
Table 14.3.3	Not part of TFL – Reserved for Narratives in CSR		
14.3.3 Clinical Lab	oratory		
Table 14.3.3.1	Listing of Abnormal Laboratory Values – Part A, B, C, D	Safety	
Table 14.3.3.2	Summary of Clinical Laboratory Data - Clinical Chemistry – Part A, B, C, D	Safety	
Table 14.3.3.3	Summary of Clinical Laboratory Data – Hematology – Part A, B, C, D	Safety	
Table 14.3.3.4	Summary of Clinical Laboratory Data – Coagulation – Part A, B, C, D	Safety	
Table 14.3.3.5	Shift Table Clinically Significant Results – Clinical Chemistry – Part A, B, C, D – if applicable	Safety	
Table 14.3.3.6	Shift Table Clinically Significant Results – Hematology – Part A, B, C, D – if applicable	Safety	
Table 14.3.3.7	Shift Table Clinically Significant Results – Coagulation – Part A, B, C, D – if applicable	Safety	

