## 7.2 Discontinuation/Withdrawal From the Study

A participant may withdraw from the study at any time at his/her own request, or may be withdrawn at any time at the discretion of the Investigator for safety, behavioral, compliance, or administrative reasons. This is expected to be uncommon.

An Investigator may discontinue or withdraw a participant from the study for the following reasons:

- Any treatment-related Grade 3 or higher AE per NCI CTCAE version 5.0 criteria
- Pregnancy (see Appendix 4 and Section 8.4.5)
- If in the opinion of the Investigator, patient with ITP is not responding adequately or for adequate duration in Part D (ie, no platelet count increase from baseline or return to

Compound: M254 Protocol: MOM-M254-001

Protocol Date and Version:8 Global 28 April 2020

baseline within 1 weeks), subject should be discontinued from the study to timely administer treatment per local standard of care.

- Protocol deviation
  - Noncompliance to intervention
  - Requires treatment not allowed in the protocol for disease flare
  - If the participant meets an exclusion criterion (either newly developed or not previously recognized) that precludes further study participation
- Sponsor decision
- Participant request to discontinue study intervention

At the time of discontinuing from the study, if possible, an early discontinuation visit should be conducted, as shown in the Schedule of Activities (Section 1.2). See activities for the final follow-up to be performed.

The participant will be permanently discontinued both from the study intervention and from the study at that time.

If the participant withdraws consent for disclosure of future information, the sponsor may retain and continue to use any data collected before such a withdrawal of consent.

If a participant withdraws from the study, he/she may request destruction of any samples taken and not tested, and the Investigator must document this in the site study records.

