#### 9.3 **Statistical Analyses**

The statistical analysis plan will be developed and finalized before database lock and will describe the participant populations to be included in the analyses, and procedures for

Compound: M254 Protocol: MOM-M254-001

Protocol Date and Version:8 Global 28 April 2020

accounting for missing, unused, and spurious data. This section is a summary of the planned statistical analyses of the primary and secondary endpoints.

All demographic, safety, PK, and PD data will be listed and summarized in tabular and graphical formats using descriptive statistics for continuous variables and frequency and percentages for discrete variables. Missing data will not be imputed.

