9.1.2 Imputation

Unless otherwise noted, data will not be imputed.

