17.2 Pharmacodynamic Summaries

17.2.1 Platelet Counts

Continuous descriptive statistics (as defined in Section 9.1.3) will be used to summarize the serum levels and changes from baseline (absolute values and percentages) by study part and treatment. Data from Part D will be summarized by planned and actual treatment (if the actual number of doses received differs from planned). CV will not be presented for changes from baseline summaries. If the total number of subjects per treatment is lower than 3 then the only descriptive statistics presented will be arithmetic mean, minimum and maximum

Linear plots of the arithmetic mean absolute values and changes from baseline (absolute and % change) by scheduled sampling time will be provided by part and treatment. For Part D these plots will be provided for both planned and actual treatment.

Linear plots of the combined individual serum levels (absolute values) and changes from baseline (absolute and % changes from baseline) by actual sampling time (spaghetti plots) will be provided by part and treatment. For Part D these plots will be provided for both planned and actual treatment.

Linear plots of the individual serum levels (absolute values) and changes from baseline (absolute and % changes from baseline) by actual time will be provided by subject.

All individual subject platelet counts and changes from baseline (absolute change and percentages) will be provided in the tables.

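### Part D planned-dose and overall FAS mean platelet profiles can rise across repeated doses through loss of non-responders alone, with no patient improving

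*SAP*

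**What the plan says.** SAP 17.2.1 asks for plots of "arithmetic mean absolute values and changes from baseline (absolute and % change) by scheduled sampling time", by part and treatment, and for Part D it wants them by planned and by actual treatment. SAP Appendix 4 lists the mean profiles, among them "Arithmetic Mean Platelet Counts Changes from Baseline versus Time Profile", as Figures 14.2.2.1.6 to 14.2.2.1.8 and the matching descriptive table as Table 14.2.2.1.1, each for FAS and PP. SAP 9.1.4 adds an overall Part D summary.

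On missing values, SAP 9.1.2 states "Unless otherwise noted, data will not be imputed" and protocol 9.3 states "Missing data will not be imputed". Each plotted mean is therefore a mean of the counts observed at that time.

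Protocol 7.2 lists, among reasons for withdrawal, that in the investigator's opinion a patient "is not responding adequately or for adequate duration in Part D". It explains this as no platelet increase from baseline, or a return to baseline within 1 week, and says such a patient should be discontinued from the study. It continues: "The participant will be permanently discontinued both from the study intervention and from the study at that time". An early discontinuation visit is held if possible.

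Platelet response after repeated M254 is a Part D secondary endpoint (protocol 3.4, SAP 5.2.1).

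**The concern.** Staying in Part D depends partly on the outcome being plotted. Patients who do not respond to the first infusion contribute to the early points and are missing from the later ones. A mean over a shrinking, increasingly responsive group can move upward although every remaining patient is unchanged. A reader of the planned-dose or overall FAS curve could take that for a response that is maintained or grows with repeat dosing. This is the question Part D is meant to inform, and the mean profile is also planned as an in-text figure of the study report (SAP Appendix 3). Neither document mentions that discontinuation depends on response.

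**Working it through.** The documents give no sample size calculation, power figure or expected withdrawal share for Part D, so there is no figure to reproduce. Two calculations show what the planned summary does when no patient changes from dose to dose.

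**1. Fixed patient values.** Inputs: n = 15 or 34 (protocol 4.1.4). Assumed: responders hold a change of +60 x 10^9/L, non-responders hold 0, and k non-responders leave after Day 8.

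Day 8 mean = 60(n − k)/n; mean from Day 22 on = 60.

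| n | k removed | Day 8 | Day 22 on | Ratio |
|---|---|---|---|---|
| 15 | 3 | 48.0 | 60.0 | 1.25 |
| 15 | 5 | 40.0 | 60.0 | 1.50 |
| 15 | 8 | 28.0 | 60.0 | 2.14 |
| 34 | 7 | 47.6 | 60.0 | 1.26 |
| 34 | 12 | 38.8 | 60.0 | 1.55 |
| 34 | 17 | 30.0 | 60.0 | 2.00 |

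The ratio is n/(n − k), the largest effect of this kind when leavers have no change at all. If everyone is kept, the mean stays at its Day 8 value (38.8 throughout for 34 patients of whom 12 do not respond). Grouped by actual doses, both curves are flat: 0 in the one-dose group and 60 in the full-course group.

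**2. Variable patient values.** Inputs from the Part C output attached to the SAP, maximum change from baseline, all subjects: M254 mean log 3.1437, between-patient variance 0.3740, residual variance 0.1970. Assumed: lognormal values, no change between doses, and removal of patients whose first-dose maximum change is below a cut-off c.

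| c (10^9/L) | Removed | Dose 1 mean, all | Dose 2 mean, remaining | Rise |
|---|---|---|---|---|
| 5 | 2% | 30.8 | 31.3 | 2% |
| 10 | 13% | 30.8 | 33.6 | 9% |
| 15 | 28% | 30.8 | 36.8 | 19% |
| 20 | 42% | 30.8 | 40.2 | 31% |

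With everyone kept, the dose 2 mean is 30.8.

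Closed-form check: with s = √(0.3740 + 0.1970) = 0.7556, the ratio is Φ[(3.1437 + 0.3740 − ln c)/s] / Φ[(3.1437 − ln c)/s]. For c = 10 this is 0.946/0.867 = 1.09; for c = 20 it is 0.755/0.578 = 1.31. Both agree with the table.

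**3. The opposing rule.** Under protocol 4.1.4, a patient whose count does not return to 100 x 10^9/L or below gets no further M254. Add an assumed share h of high responders at +120 to calculation 1, with 20% non-responders:

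- h = 20%: Day 8 mean = 60(0.6) + 120(0.2) = 60. The later mean is 60 if high responders are absent from later scheduled times, and 60/0.8 = 75 if they are still counted.
- h = 30%: Day 8 mean = 60(0.5) + 120(0.3) = 66. The later mean is 60 if they are absent, and 66/0.8 = 82.5 if counted.

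The curve can therefore rise, stay level or fall with no patient changing.

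**The case against.** The SAP already plans several outputs that bear on this.

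- **Response rate.** Table 14.2.2.1.5 lists Part D on the FAS, and percentages are based on patients exposed (SAP 9.1.3), so leavers stay in the denominator. This stands. However, SAP 17.2.2.2 defines response as reaching the therapeutic count, so the table shows whether response ever occurred and not whether it persisted over infusions.
- **Visibility of the loss.** Descriptive statistics include n, disposition gives reasons for withdrawal, and individual and spaghetti plots are planned. These reveal attrition but do not correct the mean, and nothing requires n on the mean figures.
- **Actual-dose and PP profiles.** A reader might infer that every Part D mean profile climbs through this loss. The documents do not support that. Actual-dose groups have fixed membership, and the PP set keeps only completers (SAP 10.4). Their limitation is different: the full-course and PP groups are selected for response and cannot stand for all treated patients.
- **Discretion.** Withdrawal rests on the investigator's opinion under a permissive lead-in, although the item itself says such a patient should be discontinued. This makes the withdrawn share unknown, not zero.
- **High counts.** The 100 x 10^9/L rule can pull later means down. This stands. Those patients are still followed for at least 28 days after their last dose, whereas patients withdrawn for inadequate response leave the study.

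A reader might also infer a large withdrawn share from the Part C M254 AUC over 14 days: exp(7.9716) = 2,897, and 2,897/336 h = 8.6 x 10^9/L. That is a geometric mean. With the printed variances (0.3807 + 0.9899) and lognormality, the arithmetic mean is exp(7.9716 + 1.3706/2), about 5,749, or 17.1 x 10^9/L. Neither figure gives the share of patients meeting the 7.2 description.

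**Conclusion.** The point holds for the planned-dose and overall FAS mean profiles of Part D and the corresponding table. Their later means can rise through loss of non-responders alone. On the Part C variances the rise is about 2% to 31% for 2% to 42% removed; factors such as 1.25 to 2.14 need leavers with essentially no change.

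These sizes rest on an assumed withdrawn share, on illustrative response values, and on Part C data whose M254 dose may differ from that in Part D. The simulation does not model the second trigger, early return to baseline.

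A reader might conclude that the profiles must be biased upward. The documents support only that they can be, since the re-dosing rule leaves the net direction open. Part D is descriptive with no hypothesis test, so this is a cheap improvement in what the repeat-dose response is read from, not an error in a formal inference.

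**What to change.** For Part D on the FAS, by planned treatment and overall, add the percentage of all dosed patients with a therapeutic platelet count (SAP 17.1.2 definition) at each scheduled time. Keep the denominator fixed, and count patients withdrawn under protocol 7.2 for inadequate response as not in response from that time on. Read the repeated-dose response from this output.

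Under each point of Figures 14.2.2.1.6 to 14.2.2.1.8, print the number observed out of the number dosed. Keep the PP and full-course profiles and label them as completers only.

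The cost is some SAP wording and one extra table or figure from platelet data already collected. SAP 3.0 also lets an added analysis be identified in the study report without a new SAP version. The downside is that a percentage is less sensitive than a mean, so the mean profiles remain as supporting displays. No clinical rule changes.
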